10.5.4 Analyses of Patient Reported Outcomes (PROs)

PROs include migraine symptom interference items and HIT-6. Change from baseline in total score (or subscale if applicable) of each PRO will be analyzed similarly as the primary analysis of primary and secondary efficacy endpoints described in the [Section 10.5.1](#) above during DBTP.

For HIT-6, in addition to the analysis of continuous change from baseline value, proportions of subject with a ≥ 5 point reduction from baseline and proportions of subject with HIT-6 ≥ 60 (severe impact) will be analyzed similarly as the primary analysis method for dichotomous efficacy endpoints described in the [Section 10.5.1](#) above.

No sensitivity analysis will be conducted for PROs.

For the OLTP of the study, descriptive summaries of PRO endpoints will be tabulated by randomized treatment group and visit based on observed data without imputation.

10.5.5 Pharmacokinetic Endpoints

The pharmacokinetic concentration of all subjects will be summarized with descriptive statistics by treatment groups and visits using PK analyses set.

For the population PK analysis, please refer to the separate population PK/PD analysis plan for details.

10.6 Safety Analyses

For safety endpoints, all randomized subjects who received at least one dose of investigational product (ie, Safety Analysis Set) will be analyzed based on the randomized treatment unless a subject has received the incorrect dose the entire period of interest (phase or study).

No statistical testing comparing treatment groups will be performed in the safety analyses.

10.6.1 Adverse Events

The Medical Dictionary for Regulatory Activities (MedDRA) version 18 or later will be used to code all adverse events (AE) to a system organ class and a preferred term. All adverse events will be graded using the Common Terminology Criteria for Adverse Events (CTCAE) Version 4. All adverse event tables will be summarized by treatment group. Refer to [Section 6.1.2](#) for the definition of treatment-emergent adverse event.

The subject incidence of AEs will be summarized for all treatment-emergent AEs (TEAEs), serious AEs, AEs leading to withdrawal of investigational product, fatal AEs, and device-related AEs for DBTP and OLTP, respectively.

Subject incidence of all treatment-emergent AEs, serious AEs, AEs leading to withdrawal of investigational product, serious AEs leading to withdrawal of investigational product, fatal AEs and device-related AEs will be tabulated by system organ class in alphabetical order and preferred term in descending order of frequency, for DBTP and OLTP, respectively.

In addition, subject incidence of all treatment-emergent AEs and serious AEs will be tabulated by system organ class in alphabetical order, preferred term and CTCAE grade in descending order of frequency, for DBTP and OLTP, respectively. Subject incidence of all treatment-emergent AEs and serious AEs will also be tabulated by preferred term in descending order of frequency.

Treatment-related treatment-emergent AEs will be summarized for OLTP by system organ class, preferred term and CTCAE grade.

In addition, exposure-adjusted incidence rate will be produced for DBTP and OLTP, respectively. All treatment-emergent AEs and serious AEs will be tabulated by preferred term in descending order of frequency.

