9.2 Safety Event Reporting Procedures

9.2.1 Reporting Procedures for Adverse Events and Adverse Device Effects That do not Meet Serious Criteria

The investigator is responsible for ensuring that all adverse events **and adverse device effects (including the OLTP and CHU substudy)** observed by the investigator or reported by the subject that occur after the first dose of investigational product through the end of the safety follow-up visit (16 weeks after the last dose of investigational product) are reported using the Event CRF (eg, Adverse Event Summary), including events that are reported to the Event Adjudication Committee for adjudication.

The investigator must assign the following adverse event attributes:

- adverse event diagnosis or syndrome(s), if known (if not known, signs or symptoms),
- dates of onset and resolution (if resolved),

- severity and/or toxicity,
- assessment of relatedness to investigational product (**AMG 334/placebo**), and/or **the Amgen medical devices (pre-filled syringe or the AI/Pen)**, and/or **study-mandated procedure/study activity**, and
- action taken.

The adverse event grading scale used will be the CTCAE. The grading scale used in this study is **available at the following location:**

http://ctep.cancer.gov/protocolDevelopment/electronic_applications/ctc.htm.

During the double-blind treatment period, the investigator must assess whether the adverse event is possibly related to the investigational **medicinal** product (**AMG 334/placebo**). This relationship is indicated by a “yes” or “no” response to the question: “Is there a reasonable possibility that the event may have been caused by the investigational **medicinal** product (**AMG 334/placebo**)?”

During the OLTP and the CHU substudy, the investigator must assess whether the adverse event is possibly related to **AMG 334**. This relationship is indicated by a “yes” or “no” response to the question: “Is there a reasonable possibility that the event may have been caused by **AMG 334**?”

During the OLTP and the CHU substudy, the investigator must assess whether the adverse event is possibly related to the prefilled syringe or AI/Pen (investigational medical devices used to administer **AMG 334**). The relationship is indicated by a “yes” or “no” response to the question: Is there a reasonable possibility that the event may have been caused by the investigational medical devices?

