10.5.5 Safety Endpoints

For safety endpoints, all randomized subjects who received at least one dose of investigational product (ie, safety analysis set) will be analyzed **according to the randomized treatment unless a subject has received the incorrect dose during the entire double-blind treatment phase.**

The Medical Dictionary for Regulatory Activities will be used to code all adverse events.

Subject incidence rates (double-blind treatment phase) and **exposure-adjusted** subject incidence rates (**OLTP**) of all treatment-emergent adverse events will be tabulated by treatment groups and by system organ class and preferred term. Tables of fatal adverse events, serious adverse events, adverse events leading to withdrawal from investigational product, treatment-related adverse events, serious treatment-related adverse events, and adverse events of special interest also will be provided.

In addition, summaries of treatment-emergent adverse events and summaries of serious treatment emergent adverse events will be provided by preferred term in descending order of frequency. The analyses of safety laboratory endpoints will include summary statistics over time by treatment group **for selected analytes**. Shift tables of the worst on-study safety laboratory toxicity based on grade relative to baseline will be tabulated by treatment group.

The analyses of vital signs will include summary statistics over time by treatment group.

The incidence and percentage of subjects who develop anti-AMG 334 antibodies (binding and if positive, neutralizing) at any time will be tabulated by treatment group.

All safety analyses will be performed for the double-blind treatment phase and **OLTP** separately.

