6.1.2 Safety Endpoints

Serious Adverse Event (SAE)

SAEs determined by the flag indicating if the adverse event is serious on the Adverse Events eCRF page will include those that occur after signing of the informed consent and up to and including end of study.

Treatment-Emergent Adverse Event

Adverse Events (AEs) recorded on the Adverse Events eCRF page that occurs on or after first dose of investigational product as determined by the flag indicating if the adverse event started prior to the first dose on the Adverse Events eCRF and up to and including 112 days after the end of investigational product (16 weeks after the last dose of IP) or end of study, whichever comes earlier.

Serious Treatment-Emergent Adverse Event

A serious treatment-emergent adverse event is an SAE considered to be treatment-emergent.

Treatment-Related Adverse Event

A treatment-related AE is defined as a treatment-emergent adverse event that is considered by investigators to have reasonable possibility that it may have been caused by IP as determined by the flag indicating if the event is caused by investigational product on the Adverse Events eCRF page.

Serious Treatment-Related Adverse Event

A serious treatment-related adverse event is an SAE considered to be treatment-related.

Columbia-Suicide Severity Rating Scale (C-SSRS)

The C-SSRS is a clinician rating of suicidal behavior and ideation. Two versions depending on the type of visits will be used in this study: Screening and Since Last Visit. The C-SSRS consists of a maximum of 20 items to evaluate suicidal behavior and suicidal ideation.

Beck Depression Inventory (BDI)-II

The Beck Depression Inventory (BDI)-II is a 21-item questionnaire that assesses severity of depression. Each item is scored from 0 to 3. The total score is categorized into 4 severity grades: minimal depression (0-13), mild depression (14-19), moderate depression (20-28), and severe depression (29-63).

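### SAP 10.6.1 plans treatment-related adverse events for the open-label phase only, and serious treatment-related events for neither phase, although Protocol 10.5.5 asks for both by phase

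*SAP*

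**What the plan says.** Protocol 10.5.5 first sets out the general adverse event tables: incidence "of all treatment-emergent adverse events will be tabulated by treatment groups and by system organ class and preferred term". It then lists further tables, ending with "treatment-related adverse events, serious treatment-related adverse events, and adverse events of special interest also will be provided". Its last sentence fixes the phases: "All safety analyses will be performed for the double-blind treatment phase and" the OLTP, each on its own.

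SAP 10.6.1 has two lists that cover both phases. The summary list closes with "AEs leading to withdrawal of investigational product, fatal AEs, and device-related AEs for DBTP and OLTP, respectively". The list by system organ class and preferred term adds one category: "serious AEs leading to withdrawal of investigational product, fatal AEs and device-related AEs will be tabulated by system organ class". Treatment-related events are in neither list. They appear once in that section: "Treatment-related treatment-emergent AEs will be summarized for OLTP by system organ class, preferred term and CTCAE grade". Serious treatment-related events and events of special interest do not appear in it.

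SAP 6.1.2 nevertheless defines the first two terms. It says "A treatment-related AE is defined as a treatment-emergent adverse event that is considered by investigators" to have a reasonable possibility of being caused by investigational product. A serious treatment-related event is a serious event meeting that definition. Neither definition is restricted to a phase. SAP Section 11, on changes from protocol-specified analyses, reads N/A.

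**The concern.** The data for a double-blind table will exist. Protocol 9.2.1 states: "During the double-blind treatment period, the investigator must assess whether the adverse event is possibly related to the investigational" product. Those judgements are made by site staff who do not know the assignment, and they are made in the same way in every arm. Set out by arm, they show how often investigators attribute events to treatment on placebo and on each dose. The placebo column shows how much attribution occurs without the drug.

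In the OLTP every subject knowingly receives AMG 334, so the same table has no such reference. The SAP therefore plans the attribution table where it is hardest to interpret and omits it where it can be read against a control. Safety is a secondary objective, and Protocol 10.4.3 includes safety compared with placebo in the aim of the week 24 primary analysis. If the table is not specified beforehand, it would have to be added after unblinding or left out of that report.

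**Working it through.** No sample size, error rate or event count is involved, so the check sets the tables required by Protocol 10.5.5 against those planned in SAP 10.6.1, by category and phase.

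| Category named in Protocol 10.5.5 | Double-blind phase in SAP | OLTP in SAP | Defined in SAP 6.1.2 |
|---|---|---|---|
| Fatal | planned | planned | – |
| Serious | planned | planned | yes |
| Leading to withdrawal of product | planned | planned | – |
| Treatment-related | **absent** | planned | yes |
| Serious treatment-related | **absent** | **absent** | yes |
| Of special interest | **absent** | **absent** | no |

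**Count.** The two relatedness categories in two phases make 2 × 2 = 4 required tables. The SAP plans 1, so 3 are absent. Events of special interest add 2 more absent tables, but for a different reason, given in the last step below.

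**Could other SAP text supply the double-blind table?**

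- The general statement in 10.6.1 that adverse event tables are summarized by treatment group settles the columns, not the phases. The relatedness sentence names the OLTP alone, while the two lists before it name both phases.
- The serious adverse event tables do not stand in for serious treatment-related events, because they are not filtered by relatedness.
- The exposure-adjusted rates cover both phases, but they are tabulated only for all treatment-emergent events and serious events.
- No other SAP section plans a relatedness table.

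**Can the missing relatedness tables be produced from what is collected?** Yes. SAP 6.1.2 takes seriousness, onset before or after first dose, and relatedness from flags on the Adverse Events eCRF. SAP 6.4 already assigns safety data to each phase through its analysis windows.

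**Which subjects would the double-blind table show?** The planned randomization is about 131 on placebo and 66 + 131 + 131 = 328 on AMG 334. The table itself would use the Safety Analysis Set, that is, dosed subjects, so the actual denominators may be smaller.

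**Events of special interest.** Protocol 10.5.5 uses the term, but neither document lists or defines the events and no eCRF flag for them is described. The nearest item is the cardiovascular and cerebrovascular adjudication in Protocol 9.3. Its definitions and preferred-term mapping are deferred to a separate document, and it is not called a list of events of special interest.

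**The case against.** The strongest objection is that little is lost. A reader might infer from the OLTP-only sentence that the placebo-controlled safety comparison has disappeared. The documents do not support that. Protocol 10.5.5 asks for tables, not tests, and SAP 10.6 plans no statistical testing between groups for safety. For the double-blind phase, by treatment group, SAP 10.6.1 keeps all treatment-emergent events, serious events, events leading to withdrawal, fatal events and device-related events, with CTCAE grade tables and exposure-adjusted rates for the main categories. Those tables carry the randomized contrast. What is missing is the subset filtered by the investigator's opinion on causality. This part of the objection stands and limits the weight of the point.

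The second objection concerns versions. A reader might take N/A in SAP Section 11 as proof of an undeclared departure. The SAP says that it implements Protocol 1.0 of June 16, 2015. The protocol supplied is Amendment 2 of 05 June 2017. Its summary of changes for 10.5.5 records no change to the sentence requiring these tables or to the sentence on separate phases, which suggests that the requirement is older than the amendment. But that summary starts from a document dated 20 August 2015, so it cannot show what the June 2015 text said. This objection also stands: the omission can be called undeclared only relative to the current protocol.

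Third, because SAP 6.1.2 defines both relatedness terms without limit to a phase, the gap looks more like a drafting omission than a deliberate choice. That is plausible, but a programmer following 10.6.1 as written would still not produce the tables.

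**Conclusion.** The point holds in a limited form. Against the current protocol, SAP 10.6.1 omits the double-blind table of treatment-related events and the tables of serious treatment-related events in both phases, which is three of the four relatedness tables required. The consequence is that the descriptive by-arm display of investigator-attributed events against placebo is not planned. The all-cause double-blind safety tables, the primary endpoint and the type I error control are unaffected, so this should be corrected but does not threaten the trial's main conclusions.

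The conclusion rests on reading the closing sentence of Protocol 10.5.5 as covering the tables listed earlier in that section, which is its plain meaning. It does not rest on Protocol 1.0, which was not available. The absence of a table for events of special interest is real but is a separate gap: the term has to be defined before any table can be specified.

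**What to change.** In SAP 10.6.1, extend the sentence on treatment-related events to both phases, with the double-blind table by randomized treatment group including placebo, under the Safety Analysis Set rule in SAP 7.3. Add serious treatment-related events by system organ class and preferred term for both phases. If the sponsor prefers not to produce any of these, say so and give the reason in SAP Section 11.

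For events of special interest, first define them or cite the document that does, then add a table for each phase.

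Cite the current protocol version when the SAP is next revised, so that Section 11 can be checked against it. The SAP still describes a 52-week OLTP, whereas the current protocol has 76 weeks, so a revision is needed in any case.

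The relatedness tables need no new data collection, only a few standard outputs from existing flags and phase windows. The special-interest tables cost somewhat more, because an event list has to be agreed, preferably before unblinding.

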10.6.2 Laboratory Test Results

Shifts tables of the laboratory toxicity for absolute neutrophil count (ANC) based on CTCAE grade relative to baseline will be tabulated by treatment group for each study phase.

Summary of change from baseline for ANC, alanine transaminase (ALT) and aspartate aminotransferase (AST) will also be provided by visit for each study phase.

Subject incidence of liver function test abnormalities (including AST, ALT, Total Bilirubin (TBL) and Alkaline Phosphatase (ALP)) will also be summarized by treatment group and study phase.

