The continuous efficacy endpoints will be analyzed using a linear mixed effects model including treatment group, baseline value, stratification factor, scheduled visit, and the interaction of treatment group with scheduled visit, without any imputation of missing data. The primary endpoint will be tested for each AMG 334 treatment group compared to the placebo group using appropriate contrasts in a closed testing procedure. The mean change from baseline for each treatment group, and the treatment difference, 95% confidence intervals, and p-value will be reported. For all efficacy endpoints, nominal p-values will be provided for the comparisons between each AMG 334 treatment group vs the placebo group without multiplicity adjustment.

Dichotomous efficacy endpoints will be analyzed using a stratified Cochran-Mantel-Haenszel (CMH) test after the missing data are imputed as non-response. The odds ratio for each AMG 334 treatment group vs placebo group and associated 95% confidence intervals will be reported. As safety analyses, subject incidence of treatment-emergent adverse events will be tabulated by system organ class and preferred term by treatment group for the double-blind treatment phase. For the OLTP, **exposure**-adjusted subject incidence rate of treatment-emergent adverse events will be tabulated overall. Measurements of safety laboratory and vital sign data will be summarized over time and laboratory shift tables will be provided.

The proportion of subjects who administer a full dose of AMG 334 in home-use will be summarized by treatment group at CHU day 29 and day 57. Subject incidence of adverse

events, serious adverse events, and adverse device effects will be summarized by system organ class and preferred term for subjects enrolled in the CHU substudies.

[figure not shown]
For a full description of statistical analysis methods, please refer to [Section 10](#).

Sponsor: Amgen Inc.

Data Element Standards
Version/Date:

[figure not shown]
Version 4, 31 October 2013

Study Design and Treatment Schema for Subjects That Completed Week 48 Under Protocol Amendment 2 (OL70 subjects)

[figure not shown]
IP = investigational product; QM = monthly; SC = subcutaneous

Study Design and Treatment Schema for Subjects Still in the Double-blind Treatment Phase Protocol Amendment 2
(OL140 Subjects)

IP = investigational product; QM = monthly; SC = subcutaneous

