7.2.19 Laboratory Assessments

Sites must use the central laboratory for subject eligibility and assessments during the study, unless stated otherwise. Laboratory samples will be processed and sent to the central laboratory which is responsible for either completing the assessment or shipping the samples to Amgen for assay, depending on the assessment. The central laboratory will be used for parameters such as complete blood count (CBC) with differential, serum chemistry, urine drug screening, and serum pregnancy testing (for women of childbearing potential [WOCBP]). Samples for PK testing, biomarker development, pharmacogenetic studies, and anti-AMG 334 antibody testing will be sent to the central laboratory and the central laboratory will forward the samples to Amgen (or designee) for analysis. Sites will locally perform the urine pregnancy testing (for WOCBP) (also indicated as "local laboratory").

Please refer to the central laboratory manual for instructions on the collection, processing, and shipping of samples.

Any sample collected according to the Schedule of Assessments (Table 2-Table 4) may be analyzed for any of the tests outlined in the protocol and for any tests necessary to ensure subject safety. This includes testing to ensure analytical methods produce reliable and valid data throughout the course of the study. This may also include, but is not limited to, investigation of unexpected results, incurred sample reanalysis, and analyses for method transfer and comparability.

See Table 5 for Analyte Listing (all run by central laboratory, unless otherwise noted as “Amgen/designee” or “local” laboratory. Please refer to the central laboratory manual for the complete listing of analytes run by the central laboratory):

Table 5. Analyte Listing

Chemistry	Urinalysis	Hematology	Other Labs
Sodium	Specific gravity	RBC	Pregnancy testing- serum
Potassium	pH	Hemoglobin	Pregnancy testing-urine (local)
Chloride	Blood	Hematocrit	Hepatitis B Surface Antigen (HepBsAg)
Bicarbonate	Protein	MCV	Hepatitis B Core Antibody (HepBcAb)
Total protein	Glucose	MCH	Hepatitis C virus antibody
Albumin	Bilirubin	MCHC	Polymerase chain reaction (reflexive)
Calcium	WBC	RDW	Urine drug screening
Magnesium	RBC	Reticulocytes	PK (Amgen/designee)
Phosphorus	Epithelial cells	Platelets	PK Substudy (optional) (Amgen/designee)
Glucose	Bacteria	WBC	Anti-AMG 334 antibodies (Amgen/designee)

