10.1.1.2 Secondary Endpoints

Efficacy:

- Achievement of at least a 50% reduction from baseline in mean monthly migraine days over the last three months (months 4, 5, and 6) of the double-blind treatment phase
- Change from baseline in mean monthly acute migraine-specific medication treatment days over the last three months (months 4, 5, and 6) of the double-blind treatment phase

Safety:

- Adverse events
- Clinical laboratory values and vital signs
- Anti-AMG 334 antibodies

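### SAP 10.6.2 limits graded laboratory shift tables to neutrophil count and declares no change, although the protocol sets no analyte limit on them

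*SAP*

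**What the plan says.** Protocol 10.1.1.2 lists "Clinical laboratory values and vital signs" among the secondary safety endpoints, and SAP 4.1.2 repeats it.

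Protocol 10.5.5 treats laboratory data in two sentences. The first plans summary statistics over time by treatment group "for selected analytes". The second reads: "Shift tables of the worst on-study safety laboratory toxicity based on grade relative to baseline will be tabulated by treatment group". The protocol synopsis (Statistical Considerations) says the same in brief: "Measurements of safety laboratory and vital sign data will be summarized over time and laboratory shift tables will be provided".

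SAP 10.6.2 plans three laboratory outputs:

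- Shift tables, produced separately per phase: "Shifts tables of the laboratory toxicity for absolute neutrophil count (ANC) based on CTCAE grade relative to baseline will be tabulated by treatment group".
- Change summaries: "Summary of change from baseline for ANC, alanine transaminase (ALT) and aspartate aminotransferase (AST) will also be provided by visit for each study phase".
- Liver tests, again split by phase: "Subject incidence of liver function test abnormalities (including AST, ALT, Total Bilirubin (TBL) and Alkaline Phosphatase (ALP)) will also be summarized by treatment group".

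SAP Section 11, which is reserved for changes from protocol-specified analyses, is marked not applicable.

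**The concern.** The SAP plans one graded shift table, for neutrophils, where the protocol plans shift tables of laboratory toxicity in general. It also leaves out that the comparison is with the worst grade reached on study, and it does not present either choice as a change.

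A worst-grade shift table shows by arm, including placebo, how many subjects moved from a normal or low grade at baseline to a higher one. Under SAP 10.6.2 no such table is planned for hemoglobin, platelets, creatinine, electrolytes or CPK, to the extent that these carry a grade. A team programming from the SAP would finish its listed outputs without producing the analysis that the protocol promised.

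**Working it through.** The plan states no figure on this point, so the check is a comparison of texts followed by a count.

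**1. What the analyte limit qualifies.** In Protocol 10.5.5 the words "for selected analytes" end the sentence on summary statistics over time. The shift-table sentence follows separately and has no such words. The synopsis has no limit either.

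**2. Protocol against SAP.**

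- Shift tables, analytes: the protocol sets no limit; the SAP has ANC only.
- Shift tables, grade compared with baseline: worst on-study in the protocol; not stated in the SAP.
- Summaries over time: selected analytes in the protocol; ANC, ALT and AST in the SAP. These agree.
- Incidence of liver test abnormalities: not itemised in Protocol 10.5.5; AST, ALT, TBL and ALP in the SAP. This is an addition.

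Only the first two lines show a departure.

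**3. Is the departure declared?** Section 11 declares none. The readable entries of SAP Section 14 (data not covered) are ECG interval data and PK. Two further entries are blacked out and nothing can be inferred from them.

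**4. Version.** The SAP is written to Protocol 1.0 of June 16, 2015; the protocol supplied is Amendment 2 of 05 June 2017. The amendment log shows the same shift-table sentence in the text that it replaced, so the amendment did not introduce the requirement. That replaced document is dated 20 August 2015, so it supports the point without being direct evidence of the June 2015 wording.

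**5. Count.** Protocol 7.2.19 says "See Table 5 for Analyte Listing". From that table:

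- Chemistry 24. Hematology 10 + 11 differential cell types + nucleated red cells = 22. Urinalysis 12.
- Chemistry and hematology: 24 + 22 = 46. With urinalysis: 46 + 12 = 58.
- With a shift table: 1/46 = 2.2%, or 1/58 = 1.7%.
- Named in any SAP 10.6.2 output (ANC, ALT, AST, TBL, ALP): 5/46 = 10.9%, or 5/58 = 8.6%.
- Not named: 41/46 = 89%, or 53/58 = 91%. With the differential reduced to neutrophils alone, 46 − 10 = 36 items and 31/36 = 86%.

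These are counts of analytes collected, not of tables missing. The protocol's tables are based on grade, and the documents do not say which items are gradable. At most 46 − 1 = 45 chemistry and hematology items lack a shift table that the protocol would call for; the true number is lower by however many have no grade.

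**The case against.** Several arguments on the other side have weight.

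- **The protocol never says all analytes, and Protocol 10.5.1 leaves details of method to the SAP.** The SAP may therefore specify the set. Even so, reducing a plural, unrestricted requirement to one analyte, without a reason, goes beyond filling in detail, and the same protocol section states an analyte limit where it wants one.
- **Other outputs carry laboratory information.** SAP 10.1 commits in general terms to descriptive statistics by treatment group at each visit. Under Protocol 9.2.1, values that need treatment or a change in therapy are adverse events, and SAP 10.6.1 tabulates these by grade. An independent DMC also reviews treatment-group safety summaries. All this stands, but none of it replaces the shift table. By-visit statistics do not show individual worst grades. Protocol 9.2.1 generally keeps abnormal values judged not clinically significant out of the adverse event data and, where there are clinical sequelae, records those in place of the abnormality. DMC review is not an output of the trial's analysis.
- **Nothing inferential depends on it.** SAP 10.6 plans no between-group safety tests. That is correct, and it limits the seriousness of the point.

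A reader might infer that most of a named safety endpoint goes unanalysed. The documents do not support that: the endpoint includes vital signs, which SAP 10.6.3 covers; the liver tests have their own outputs; and the general commitment in SAP 10.1 remains. A reader might also count the short change-from-baseline list as a departure. It is not one, because the current Protocol 10.5.5 allows selected analytes there.

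**Conclusion.** The point holds as an undeclared difference in scope between protocol and SAP. Protocol 10.5.5 requires worst on-study grade shift tables with no analyte limit; SAP 10.6.2 plans them for ANC only and does not specify the worst grade. Apart from ANC and the liver-test outputs, SAP 10.6.2 plans no graded laboratory output by arm.

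The size can be stated only in analytes: one of 46 chemistry and hematology items has a shift table, and five are named in any laboratory output of that section. Treating each of the remaining items as a missing table would go further than the documents allow.

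The conclusion assumes that the shift-table sentence is read as written, without carrying over the limit from the sentence before it. It does not affect the primary efficacy analysis or any test. It should be corrected because the SAP as written would not produce a safety analysis that the protocol commits to.

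**What to change.** Extend SAP 10.6.2 to shift tables of the worst on-study CTCAE grade relative to baseline for the gradable chemistry and hematology analytes in Protocol Table 5, by treatment group and study phase, and state worst on-study for ANC as well. If the sponsor intends a restricted set, name the analytes in SAP 10.6.2, give the reason, and record the change in SAP Section 11. The protocol does not prescribe the full gradable set in so many words, so either route settles the difference.

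The cost is a few additional standard tables. The samples already go to a central laboratory (Protocol 7.2.19), SAP Appendix C already adopts CTCAE grading for laboratory toxicity, and SAP 9.7 provides for validated standard macros. No new data are needed, and no multiplicity question arises because safety outputs are not tested.
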